Title: Patient-Centered, Interprofessional Approach to Improve Functional Outcomes in a Skilled Nursing Facility

NCT04300413

Version Date: 01.28.2020

IRB Approval Date: 03.04.2020

COMIRB Protocol
COLORADO MULTIPLE INSTITUTIONAL REVIEW BOARD
[name] [contact] [contact]

Protocol #: 19-2490

Project Title: Patient-Centered, Interprofessional Approach to Improve Functional Outcomes in a Skilled Nursing Facility

Principal Investigator: [name], MPT, PhD

Version Date: 01.28.2020

I. Hypotheses and Specific Aims:

For many older adults, a skilled nursing facility (SNF) stay is required to address functional deficits stemming from hospitalization. However, during a typical SNF stay, patients receive rehabilitation for 1-2 hours of their day and remain sedentary for up to 14 waking hours, which is not reflective of the mobility levels needed to thrive in the community.¹⁻³ While a previous high-intensity strengthening intervention implemented by our group (COMIRB Protocol #: 14-2388, Intensive Therapeutic Rehabilitation for Older Skilled Nursing Home Residents: i-STRONGER) demonstrated superior outcomes when compared to usual care, the benefits of rehabilitation are likely negated by sedentary behavior outside of structured rehabilitation time. We propose that an interprofessional movement program combined with i-STRONGER strengthening will be feasible, acceptable, and will lead to superior patient outcomes.

AIM 1: Determine the feasibility and acceptability of implementing a structured mobility program High-Intensity Rehabilitation plus Mobility (HeRo) for SNF residents and staff

H1: HeRo will be acceptable to SNF residents: SNF residents will score $\geq 70\%$ in the patient satisfaction survey and will indicate acceptability in semi-structured interviews. HeRo will also be feasible, as evidenced by $>90\%$ treatment fidelity scores by providers.

AIM 2: Determine the effectiveness of HeRo for improving patients' gait speed, short physical performance battery (SPPB), and physical activity levels (i.e. upright time, steps per day) compared to a) the usual care group and b) the i-STRONGER only group.

H2: Patients who participate in HeRo will demonstrate greater gains in gait speed, SPPB, and physical activity over the course of a SNF stay when compared to the usual care group and the i-STRONGER only group.

II. Background and Significance:

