Physical activity will be measured using the ActivPAL device (PALTechnologies: Glasgow, Scotland), which effectively measures sedentary time and steps per day. The ActivPAL is a small device which is attached to the participant's thigh for up to seven days at a time. This is a small (35x53x7mm) and lightweight (15 grams) device that uses accelerometer-derived information about thigh position to estimate time spent in different body positions (i.e., sitting/lying, standing, and stepping). The device is positioned on the midline of the thigh, ~1/3 between the hip and knee. The device is placed in a small nitrile sleeve and attached using a non-allergenic adhesive pad and thus can be worn during bathing and overnight, allowing for continuous measurement. Participants will be instructed to wear the monitor on their leg for up to ten consecutive days at all times except when submerged in water (e.g., bath and shower is acceptable). The time-stamped "event" data file from the ActivPAL software will be used to determine time spent sitting/lying, standing and stepping per day. Using a customized R program,³⁸ the event data file will be converted to a sec-by-sec file and additional metrics of sedentary behavior

(e.g., total time participating in activity, average duration of sedentary bouts) will be estimated. The ActivPAL has been validated for use in older and middle aged adults with very high levels of accuracy (99-100%)³⁹⁻⁴¹

Feasibility and acceptability (Aim 1) will be assessed by patient surveys, fidelity assessments, and semi-structured interviews. Treatment fidelity will be assessed throughout the duration of the study by objective check lists for the mobility coach including 1) mobilization of patients.2) application of principals of behavioral economics and 3) safe patient handling techniques. Fidelity assessments will also be performed for i-STRONGER on PTs, PTAS, COTAs, and OTs to ensure appropriate application of principals of i-STRONGER. Fidelity checks will be performed by [name] or [name] one time per week and monthly thereafter as long as fidelity remains above 90%. Patient acceptability will be assessed through semi-structured interviews and analyzed using rigorous qualitative methods. Twenty-two participants will participate in interviews, and participation in interviews will be voluntary. Interview participants will be recruited using purposive sampling from the total sample of participants.

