Outcomes data will only be collected on patients who fit the inclusion criteria: adults 18 through 120 years of age who are admitted to a skilled nursing facility, receive at least physical therapy and were ambulatory prior to hospitalization Exclusion criteria: Patients with neurological disorders, such as a acute stroke or acute traumatic brain injury, will be excluded as the best practice for managing these patients is based on motor-control theory versus the progressive strengthening and aerobic approach. Patients on hospice care will be excluded as hospice care is focused on palliative needs and not rehabilitation. Other patients to be excluded will include those with conditions where strength training is contraindicated (as indicated by the American College of Sports Medicine Guidelines for Exercise Testing and Prescription): recent unstable fractures, advanced congestive heart failure (ejection fraction <30%), bone metastasis sites, tumors in strengthening target areas, acute illness, recent myocardial infarction (within 3-6 weeks), weight bearing restrictions on graft or fracture sites, exposed tendon or muscle, absence of pedal pulses, presence of a fistula, and platelet levels <50,000/ μ L.

C. Study Design and Research Methods

This study is a preliminary investigation using a three-stage, pre-post training designs in one SNF (Figure 1). Stage 1 (usual care) and Stage 2 (i-STRONGER) have already been completed (manuscript in preparation; COMIRB #14-2388). Given that the average length of stay in a SNF is 21 days, the pre/post design will consist of three independent samples of patients to include only those that were admitted and discharged within a discrete period. During the 2 year Stage 3 (HeRo) period we will implement the interprofessional mobility program.

[figure not shown]

Figure 1. Study design

Consenting

Patients will provide written informed consent prior to participating in the study. Potentially eligible patients will be identified upon admission by PTs, OTs, SLPs, PTAs, and COTAs at the research site who have a treating relationship with the potential participant. The clinicians will describe the study to potential participants. If the patient is interested, they will sign a HIPAA A form. Following this, a professional research assistant (PRA) or [name] will screen the patient for eligibility and will approach the patient for consenting within the first 4 days of admission to the SNF.

Intervention:

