Intervention *Mobility program*

Participants in the study will participate in a regular, structured mobility program outside of rehabilitation time, guided by a mobility coach (a licensed certified nursing assistant [CNA] or physical therapist assistant [PTA]). In current SNF clinical practice, CNAs and PTAs regularly perform walking and other physical activities with patients, so this does not provide any additional risk to the participant. The CNA or PTA will be an employee of the University and a study team member included on the Personnel Form. A Professional Services Agreement between the University and the Veterans Community Living Center at Fitzsimmons will ensure adequate liability coverage, and will outline the services that the mobility coach will provide to the facility. In addition, the mobility coach will obtain Workers without Compensation (WOC) status through the Veteran's administration prior to providing the intervention.

During the first three days of the skilled nursing facility stay, the patient will wear an activity monitor (the Accusplit) to establish baseline level of mobility (i.e. steps per day) in the intervention in order to set and monitor goals, and provide patient feedback. The Accusplit is an inexpensive, non-invasive activity monitor that has been shown to have the best accuracy of commercially-availability activity monitors for older adults with slow gait speed.⁴⁵ Concurrently, patients will wear an ActivPAL device to monitor activity levels as an outcome for the study. Participants will not receive feedback directly from the ActivPAL, but it will be used for data collection as it is a more reliable and detailed measure of physical activity than the Accusplit.

Following the baseline period, the patient will select two goals: a daily step count goal/range for the remainder of the week, between 33-55% increase in step counts as well as a functional goal related to mobility and participation in life roles and activities (i.e. walking to the activity room or dining room twice per day, walking outdoors) or a goal related to time spent out of bed. Patients will keep a diary of activities performed outside of bed, which the mobility coach will review with the patient daily.²⁷ Patients will sign a pre-commitment contract in order to enhance accountability for reaching goals.

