Treatment fidelity visits will be scheduled using a fidelity checklist. Fidelity visits will be conducted by [name] or [name] with the mobility coach to ensure 1) adequate dosage of mobility (to patient tolerance, 2x day) 2) adherence to utilization of principals of behavior change and 3) safe patient handling techniques. Fidelity will be assessed 1 x per week with the mobility coach until scores reach 90%, after which fidelity assessments will occur monthly. Fidelity will also be assessed by weekly documentation audits.

Comparison groups: Previous standard of care and i-STRONGER alone

Patients in the comparison arm of the study have received usual care as per the previous standard of care prior to the i-STRONGER implementation, or the i-STRONGER alone as mentioned above. We will compare the HeRo intervention to historical data we have collected on the previous standard of care and the i-STRONGER in Stage 1 and Stage 2 in COMIRB 14-2388.

Outcome measures

Outcome measures as listed above will be assessed at admission and discharge. ActivPAL monitoring will take place throughout the course of the SNF stay to determine the magnitude of change in activity levels from admission to discharge. A PRA will perform phone calls at 7 days and 60 days following discharge from the skilled nursing facility. Information collected at phone calls will include 1) Falls, ER visits,

rehospitalizations and 2) Life-space mobility assessment. This cannot be used as an outcome measure as it was not collected with our historical data. However, this will help us to determine responders and non-responders to treatment on a longitudinal scale.

D. Description, Risks and Justification of Procedures and Data Collection Tools:

Veteran data will be managed and stored on CCTSI RedCap and VA server.

The addition of the physical activity monitor does not pose increase falls risk to the patient. There is a possibility of skin irritation from the adhesive used to affix the ActivPAL, but we will use a hypo-allergenic adhesive pad, patient education, and frequent monitoring to reduce the risk of skin irritation at the site of the ActivPAL.

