There is no expectation that the mobility program will cause serious cardiovascular responses or will increase risk of falls. Gardner et al⁴⁸ reviewed controlled clinical trials with exercise interventions for older adults at-risk for falling. No cardiac events or falls were reported in the 12 clinical trials reviewed. A similar mobility program implemented in the acute care setting demonstrated that the group that received the intervention had fewer falls than the control group.²⁷

E. Potential Scientific Problems:

Missing Data. All patients with outcome measurements will be included in the intent-to-treat analysis. Although we will encourage patients to be fully compliant to their assigned treatment regimen, they will not be dropped from follow-up measurements for lack of compliance. Although statistical methods can be used to “adjust” for missing data, these methods rely on the untestable assumption that data are “missing at random” so that the effect of the missingness can be removed through statistical modeling. We will instead focus on preventing missed follow-up visits and evaluate missingness to determine whether the data are consistent with the hypothesis of missing at random or missing completely at random.

Patient population: The SNF population is highly heterogeneous and often demonstrates fluctuations in medical status and is at risk for rehospitalizations. This heterogeneity will lead to variability in data, which will try to address by controlling for variables such as gender, age, and comorbidities.

F. Data Analysis Plan:

Aim 1 analysis: The proportion of patients in the HeRo group with a score of $\geq 70\%$ on the satisfaction survey will be compared to the null value of 75% using a one sample binomial proportions test. In addition, treatment fidelity checklist scores will be compared to the null value of 90% using a one sample binomial proportions test. For the qualitative component, verbatim transcripts will be independently coded by two study team members. Themes will be developed from those codes as an iterative process until consensus is reached among team members.

Aim 2 primary analysis: The primary analysis will be an intent-to-treat comparison of the differences among treatment groups in change in gait speed at time of SNF discharge. Statistical inference regarding the difference between treatment groups will be based on the estimated coefficient for a treatment group indicator variable in a linear regression

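### Minor, Aim 1 only: the fidelity test treats clustered checklist scores as binomial data and does not say what one trial is

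*Combined protocol and SAP*

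**What the plan says.** H1 (section I) takes more than 90% "treatment fidelity scores by providers" as the evidence of feasibility. For the test, the Aim 1 analysis in section IV.F says "treatment fidelity checklist scores will be compared to the null value of 90% using a one sample binomial proportions test". The sentence before it, on satisfaction, is complete: it starts "The proportion of patients in the HeRo group with a score of" 70% or more and sets a null of 75%, so the trial is a patient and the pass mark is given. The fidelity sentence gives only the null value.

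Other sections describe the data but not how they enter the test:

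- Outcome Measure(s) (IV.A) describes checklists for the mobility coach in three content areas, and adds: "Fidelity assessments will also be performed for i-STRONGER on PTs, PTAS, COTAs, and OTs". Checks there are "one time per week and monthly thereafter as long as fidelity remains above 90" percent.
- Treatment fidelity (IV.C) schedules weekly checks "with the mobility coach until scores reach 90%, after which fidelity assessments will occur monthly", and adds weekly audits of documentation.
- Study Design (IV.C) gives the duration: "During the 2 year Stage 3 (HeRo) period we will implement the interprofessional mobility program".

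The number of items per checklist, the significance level and the sidedness are not stated.

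**The concern.** A one-sample binomial test needs a count of independent yes/no trials, and a percentage score is not such a count. Two readings fit the text.

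- **Item as trial.** All items from all visits are pooled and the proportion achieved is tested against 90%. This addresses H1, but items scored at one visit on one coach probably succeed or fail together, and the binomial variance ignores that.
- **Visit as trial.** Each visit passes or fails at a score above 90%, by analogy with the satisfaction test. This discards most of the information and tests a different claim, namely that more than 90% of visits exceed 90%.

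At stake is H1's only stated numerical criterion for feasibility. It is also unclear whose scores count: the coach's alone, or also those of the i-STRONGER therapists, and whether the documentation audits enter.

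**Working it through.** The plan gives no sample size or power for this test, so there is no figure to reproduce.

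**Inputs.** Null 90% (IV.F). Two years of monthly coach visits, 2 × 12 = 24 (IV.C). Assumed, because not given: an exact test at one-sided 0.05 (H1 is directional), 3 to 30 yes/no items per visit, and a within-visit ICC of 0, 0.05 or 0.10.

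**Item as trial: false positives at true fidelity 90%.** With m items per visit, N = 24m. The test rejects at the smallest r with P(X ≥ r | N, 0.90) ≤ 0.05. Clustering multiplies the variance by 1 + (m − 1) × ICC. At ICC 0.05 that is 1 + 9 × 0.05 = 1.45 for 10 items, 1.95 for 20 and 2.45 for 30. Beta-binomial simulation with 100,000 runs per cell gives:

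| Items | r / N | ICC 0 | ICC 0.05 | ICC 0.10 |
|---|---|---|---|---|
| 5 | 114/120 | 4% | 5% | 7% |
| 10 | 224/240 | 5% | 8% | 12% |
| 20 | 444/480 | 4% | 10% | 15% |
| 30 | 662/720 | 4% | 14% | 20% |

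**Item as trial: power at true fidelity 95%, independent items.** P(X ≥ r | N, 0.95) is 30% (3 items), 61% (5), 83% (8), 90% (10) and 99% (20). With 10 items at two-sided 0.05 it is 78%.

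**Visit as trial.** If all n visits pass, the p-value is 0.9^n: 0.9^24 = 0.080, 0.9^28 = 0.052, 0.9^29 = 0.047. Below 29 visits the test cannot reject, whatever the checklist length or pass mark.

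From 29 visits on, success depends on the chance that a visit scores above 90%. At 95% fidelity with 10, 20 and 30 items this is P(X ≥ 10 | 10) = 0.60, P(X ≥ 19 | 20) = 0.74 and P(X ≥ 28 | 30) = 0.81, all below the 0.90 null. At 29 visits success is then at most 0.81^29 = 0.002. The most favourable checklist length between 3 and 30 is 21 items, where 19 of 21 passes: the visit pass probability is 0.915 and 0.915^29 is about 0.08.

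Solving P(visit passes) = 0.90 shows what this reading tests. For 10, 20 and 30 items the null corresponds to true fidelity of 99.0%, 97.3% and 96.3%.

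**Alternative.** Let p̄ be the mean of the 24 visit scores and s their standard deviation. The lower limit is logit(p̄) − t × (s/√24) / [p̄(1 − p̄)], where t is the one-sided 95% value on 23 df. H1 is met if this exceeds logit(0.90). In the same simulation with 10 to 30 items, false positives are about 4-5% at ICC 0, 5-6% at ICC 0.05 and 5-6% at ICC 0.10.

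Power at 95% fidelity, 10 / 20 / 30 items:

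| ICC | Log-odds limit | Binomial test |
|---|---|---|
| 0 | 87 / 99 / >99% | 90 / 99 / >99% |
| 0.05 | 71 / 85 / 90% | 86 / 96 / 99% |
| 0.10 | 60 / 71 / 75% | 84 / 93 / 96% |

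**The case against.** The strongest reply has three parts. First, the fidelity sentence compares scores with 90%, and H1 is also worded as a score, so the item reading is the intended one and the visit reading is built by analogy, with a pass mark that the analysis sentence never mentions. Second, the inflation under the item reading then rests wholly on ICCs that the documents do not give, and with a short checklist it nearly disappears. Third, this is a preliminary study with no go/no-go rule tied to the p-value, and feasibility can be judged from the reported scores; one sentence naming the unit would do.

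Much of this stands. The item reading is the more natural one, the ICCs are assumptions, and the consequence is small. Naming the unit is not enough, though: the item reading still leaves clustering unaddressed, and the visit reading still leaves a test that cannot reject at the planned monthly frequency.

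Stronger inferences are tempting, and the documents do not support them:

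- That the item test would succeed about 90% of the time or more at 95% fidelity. This needs roughly 10 or more items per visit and a one-sided test, and neither is stated.
- That a coach delivering 95% could never meet the visit criterion. This is strict only below 29 visits. IV.A implies that weekly checks could resume after a low score, which would add visits.
- That the unit would be chosen after the scores are seen. The plan is silent on when it would be settled.
- That the change from weekly to monthly checks biases the result in favour of H1. Extra visits after a low score can only pull an equally weighted mean down, which is conservative for H1.

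**Conclusion.** The concern holds as a minor point on Aim 1. The plan applies a binomial test to percentage scores, does not define the trial, and does not say whose scores count. Under the natural item reading, the false-positive rate at true fidelity 90% is about 8-14% at ICC 0.05 and 12-20% at ICC 0.10, for 10 to 30 items and 24 visits; with 5 items it is about 5-7%. Under the visit reading the test cannot reject below 29 visits and rarely succeeds at 95% fidelity above that.

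The visit-level limit follows from the null value and the assumed one-sided 0.05 level. The item-level figures rest on the assumed item count and ICC, so they show the direction and plausible size of the problem, not its actual size in this study. Gait speed and the other Aim 2 analyses are unaffected.

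**What to change.** Amend the Aim 1 analysis in two or three sentences:

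- Replace the binomial test with the mean checklist score over all coach visits, equally weighted, and a one-sided 95% lower limit on the log-odds scale with its standard error from visit-to-visit variation. H1 is met if the limit exceeds 90%. Say what happens if every score is 100%, where the log-odds is undefined; the simulation counted that as met.
- State that the HeRo criterion uses the mobility coach's checklist visits. Report the i-STRONGER therapist checks and the documentation audits separately.
- Do not reduce visits to pass or fail. Weighting visits by the time since the previous one is not needed.

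The cost is power. At 95% fidelity, 24 visits, 10 to 30 items and ICC 0.05, the probability of meeting H1 falls to about 71-90%, from about 86-99% with the binomial test, whose higher figure comes partly from its inflated error rate. No extra visits or data are needed.

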Falls, rehospitalizations, ER visits, and the life-space mobility assessment will be assessed by self-report through two follow-up phone calls: one 7 days following discharge and one 60 days following discharge. These will not be considered as an outcome measure as we do not have this information from our historical comparison group but this will help us to 1) identify responders and non-responders to the treatment and 2) generate preliminary data regarding the potential role of mobility in determining adverse events such as ER visits and rehospitalization.

Covariates, clinical and background characteristics. Information on other patient characteristics to describe the patient population and interpret results will be obtained from facility medical records. These characteristics include age; sex; race; history of comorbidities; medications; primary diagnosis for hospital admission; medical record number; prior level of function; length of skilled nursing facility stay; complications in hospital; and hospital length of stay. SNF staff will administer the Brief Inventory of Mental Status (BIMS) to assess baseline cognitive status within 24-48 hours of admission to SNF in accordance with current standard of practice.

NIH PROMIS measures will also be completed in order to characterize this population and potentially to identify responders and non-responders to HeRo. NIH PROMIS measures are well-validated, patient-reported outcome measures of physical, mental and social health. PROMIS uses computer adaptive testing (CAT) to improve precision and decrease tester and participant burden.⁴² The following CAT PROMIS measures will be assessed upon admission to and discharge from the SNF:

- Physical Function for Samples with Mobility Aid Users
- Sleep Disturbance
- Self-efficacy (Activities of Daily Living)
- Fatigue
- Satisfaction with Participation in Social Roles
- Social isolation

The Life-Space Mobility Assessment is a self-report measure assessing a patient's movements, extending from within the home to movement beyond a patient's town or

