model with change in gait speed as the response variable, and explanatory variables that include an indicator of treatment group and the baseline value of gait speed. The baseline gait speed value is included to improve the precision/power of the inference about treatment differences. The conclusion about the statistical significance of differences between groups will be determined by this single statistical test to protect against an elevated risk of false-positive conclusions. Sensitivity analysis will be done to evaluate whether conclusions would differ when other important covariates are added to the model (age, gender, comorbidities). We will model gait speed change as a function of treatment group (categorical Stages 1, 2 and 3), controlling for the baseline value of function, study stage, sex, age, length of stay, total therapy minutes, and potential confounders.

Aim 2 Secondary Analysis: Differences between groups in SPPB, falls, successful discharge to the community at time of discharge from SNF will be analyzed as described above. Secondary analyses will be evaluated for their consistency with the conclusions of the primary endpoints. We anticipate that group differences in secondary measures will be correlated with the primary so that significant differences in the primary endpoint will be reinforced by similar effects on secondary endpoints. This approach will reduce the risk of false-positive conclusions resulting from multiple statistical tests.

Sample Size Estimates

Statistical power was estimated based on measurements of gait speed change from admission to discharge on patients in both Stage 1 and Stage 2 (data collection complete, N=80). For the primary outcome (change in gait speed), we used the standard deviation of 0.28. A sample size of 155 patients (75 in Stage 3 [i.e HeRo]) will provide 80% power to detect a clinically meaningful difference in change of 0.16 m/sec between Stages 1 & 3 (primary analysis). In our previous research, 2/3rds of patients met the inclusion criteria at any given time. With an average length of stay of 21-25 days in SNFs, we should have no difficulty enrolling 75 patients for this study.

G. Summarize Knowledge to be Gained:

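### The deciding Aim 2 regression makes no provision for unequal residual variance; at group sizes of probably about 1:2, its default standard error could mislead if the stages differ in spread

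*Combined protocol and SAP*

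**What the plan says.** Section IV.F (Data Analysis Plan, Aim 2 primary analysis) bases inference on the group difference as follows: "based on the estimated coefficient for a treatment group indicator variable in a linear regression". The regression is specified as a "model with change in gait speed as the response variable, and explanatory variables that include an indicator of treatment group and the baseline value" (baseline gait speed). The same paragraph makes this test decisive: "The conclusion about the statistical significance of differences between groups will be determined by this single statistical test". The stated reason is to limit false-positive conclusions. The sensitivity analysis adds covariates (age, gender, comorbidities). No variance estimator, residual check or alternative standard error is named, and equal variance is not stated as an assumption either.

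The paragraph then describes a second, larger model: "We will model gait speed change as a function of treatment group (categorical Stages 1, 2 and 3", with further covariates.

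Under Sample Size Estimates, the SD was taken from patients in Stages 1 and 2 (N=80 together): "we used the standard deviation of 0.28". The power statement reads "A sample size of 155 patients (75 in Stage 3 [i.e HeRo]) will provide 80% power", for a difference of 0.16 m/s between Stages 1 and 3. The split of the 80 between Stages 1 and 2 is not given, nor is an SD for any single stage.

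Section IV.C describes three independent samples from successive periods at one facility, with Stages 1 and 2 already complete.

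**The concern.** The ordinary standard error of a group coefficient uses one residual variance for all groups. With equal group sizes this does little harm when the variances differ. With unequal sizes the error is systematic: the standard error is too large if the bigger group is the more variable one, and too small if it is the less variable one.

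In a randomised trial, a treatment with no effect on any patient would leave the variances equal. That protection is absent here. The stages are samples from different periods, so their spread may differ even if HeRo does nothing, and the planning SD carries no information about Stage 3. At stake are the size of the one test meant to guard against false positives, if Stage 3 is less variable than Stage 1, and some avoidable loss of power, if it is more variable.

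**Working it through.** **Inputs.** From the protocol: difference 0.16 m/s, SD 0.28, 75 in Stage 3, 80 in Stages 1 and 2 together, power 80%. Assumed: alpha 0.05 two-sided (not stated); Stage 1 size 36 to 40; all SD ratios; Stage 1 residual SD 0.28.

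**1. Reproduce the stated power and infer the Stage 1 size.** Power ≈ Φ(0.16/SE − 1.96), with SE = 0.28·√(1/n₁ + 1/75).

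- n₁ = 36: SE = 0.28·√(0.02778 + 0.01333) = 0.0568; power = Φ(2.818 − 1.96) = 80.5% (79.8% with the noncentral t).
- n₁ = 40 (even split of 80): SE = 0.28·√(0.025 + 0.01333) = 0.0548; power = 83.1% (82.5% with the noncentral t).

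The stated 80% reproduces with about 36 in Stage 1. Both values put the comparison near 1:2 (75/36 = 2.08; 75/40 = 1.88).

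**2. Distortion of the pooled standard error.** True SE = √(s₁²/n₁ + s₃²/n₃). Pooled SE = √[v(1/n₁ + 1/n₃)], with v = ((n₁−1)s₁² + (n₃−1)s₃²)/(n₁+n₃−2).

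Example with 40 versus 75 and ratio 1.5 (s₃ = 0.42):

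- True SE = √(0.0784/40 + 0.1764/75) = 0.0657.
- v = (39·0.0784 + 74·0.1764)/113 = 0.1426.
- Pooled SE = √(0.1426·0.03833) = 0.0739, which is 13% too wide.

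At ratio 0.67 (s₃ = 0.1876), the true SE is 0.0493 and the pooled SE 0.0438, which is 11% too narrow.

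**3. Simulated effect on the planned test.** Baseline-adjusted regression, 40 versus 75, 8,000 runs per cell:

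| SD ratio, Stage 3/Stage 1 | Type I error, default | Type I error, HC3 | Power at 0.16, default | Power at 0.16, HC3 |
|---|---|---|---|---|
| 0.67 | 8.5% | 5.4% | 93% | 89% |
| 0.8 | 6.8% | 4.9% | 90% | 87% |
| 1.0 | 5.4% | 5.0% | 83% | 82% |
| 1.25 | 3.4% | 4.2% | 71% | 75% |
| 1.5 | 2.9% | 4.8% | 58% | 66% |

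Monte Carlo error is about 0.2 to 0.3 points on type I error near 5% and about 0.5 points on the lower power figures. Repeating the runs with 60,000 per cell gave power gaps of about 3 and 8 points at ratios 1.25 and 1.5. The higher default power at ratios below 1 comes with the inflated type I error and is not a real gain. With 36 in Stage 1, the formula in step 2 gives type I errors of 8.4% at ratio 0.67 and 2.3% at ratio 1.5.

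**4. The other comparisons the text allows.** In a three-stage model (40/40/75, Stage 2 SD also 0.28), the pooled SE is 5% too narrow at ratio 0.67 and 6% too wide at 1.5, with type I errors of 6.0% and 3.6%. Against all 80 historical patients as one group, the pooled SE stays within about 1% of the true value at ratio 1.5.

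**5. What a mixed response would do.** Suppose half of HeRo patients gained 0.32 m/s and half gained nothing (mean 0.16). The Stage 3 variance would be 0.0784 + 0.5·0.5·0.32² = 0.104, so SD 0.322 and ratio 1.15. The default SE would be 4% too wide, and power 76% against 77% with HC3. If a quarter gained 0.64, the variance would be 0.0784 + 0.25·0.75·0.64² = 0.1552, SD 0.394 and ratio 1.41, with power 62% against 69%.

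**The case against.** The strongest reply is that nothing in the documents shows the variances to differ. At equal SDs the default test behaves as intended, and naming no variance estimator is ordinary in a self-described preliminary investigation. That stands, and it makes the point conditional.

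A reader might infer that the plan itself forecasts unequal variances, because it hopes to "identify responders and non-responders to the treatment". It does not. Section IV.A ties that phrase to the follow-up calls, which are not outcome measures, and only as a possibility to the PROMIS measures. It is no prediction about gait speed change. Likewise "This heterogeneity will lead to variability in data" in Section IV.E describes the facility population in general, not one stage more than another.

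Nor would a responder mixture, added independently of other variation, produce false positives. It widens the larger group, so the default test becomes conservative; and if HeRo helped nobody, it would add no variance at all. Excess false positives need Stage 3 to be less variable than Stage 1, for which no passage gives evidence. An assumed pair such as 0.33 and 0.24 has a further difficulty. If 0.28 is the pooled SD of Stages 1 and 2, a Stage 1 SD of 0.33 would require a Stage 2 SD of about 0.22 to 0.23.

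It is also fair that most of the power loss at higher ratios is real extra variance. From ratio 1.0 to 1.25 the default test falls from 83% to 71%, and HC3 restores only about 3 to 4 of those 12 points.

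What the reply does not remove is that the listed sensitivity analysis only adds covariates, and so would neither reveal nor correct unequal variance in samples drawn from different periods.

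**Conclusion.** The point holds in conditional form and is minor. The deciding regression has no provision for unequal residual variance, and at about 36 to 40 versus 75 its default standard error is sensitive to it. Over assumed SD ratios of about 0.7 to 1.5, type I error would range from about 8% to about 3%, with about 3 to 8 points of power forgone relative to HC3 at ratios of 1.25 to 1.5. The SE distortion is about half as large in the three-stage model.

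These figures rest on an assumed Stage 1 size, an assumed two-sided 5% level and assumed SD ratios. The documents do not support saying that the intervals will be wrong, or that the plan breaches its own protection against false positives. They support only that equal spread is neither guaranteed by the design nor checked by the analysis.

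**What to change.** In Section IV.F, keep the model and its coefficient. Add one sentence stating that the p-value and confidence interval will use a heteroscedasticity-consistent (HC3) standard error, or alternatively a residual variance fitted separately for each stage. Make the choice before Stage 3 data are seen. Report the residual SD by stage; those for Stages 1 and 2 can be examined now, since their data are complete. Under Sample Size Estimates, state the Stage 1 size and say that the 80% power assumes SD 0.28 in Stage 3 as well.

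The cost is a few sentences and one software option, plus about one point of power if the variances prove equal (83% against 82% in the simulation). HC3 corrects only the standard error; it does nothing about confounding by period.
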